At the end of the treatment induction period (Week 12), the subjects randomized to 30 mg or 60 mg M1095 who do not achieve an IGA score of 0 or 1 will be dose-escalated to 120 mg Q4W at Week 12.

Subjects who enter the maintenance/escalation period will receive one of the following treatments until Week 24 and before the dose injection at Week 24:

- **Placebo at weeks 0, 1, 2, 3, 4, 6, 8, 10** and M1095 120 mg at weeks 12, 14, 16 and Q4W.
 - **M1095 30 mg at weeks 0, 2, 4, 8, 12** and Q4W
 - **M1095 60 mg at weeks 0, 2, 4, 8, 12** and Q4W
 - **M1095 30 mg at weeks 0, 2, 4, 8** and M1095 120 mg at week 12 and Q4W
 - **M1095 60 mg at weeks 0, 2, 4, 8** and M1095 120 mg at week 12 and Q4W
 - **M1095 120 mg at weeks 0, 2, 4, 8, 12** and Q8W
 - **M1095 120 mg at weeks 0, 2, 4, 6, 8, 10, 12** and Q4W
 - **Secukinumab 300 mg at weeks 0, 1, 2, 3, 4, 8, 12** and Q4W.
- } if IGA_{Week12} ≤ 1
- } if IGA_{Week12} > 1

At the end of the maintenance/escalation period (Week 24), any subjects on M1095 treatment groups who did not undergo dose escalation at Week 12 and achieve an IGA score of 0 at Week 24 will have the study treatment withheld. To maintain the blinding after Week 24, these subjects will receive placebo Q4W. Subjects receiving secukinumab in the first treatment period will continue to receive it at the same dose 300 mg Q4W throughout the study.

[figure not shown]
Subjects who enter the response assessment/dose hold period will receive one of the following treatments until Week 44 (or until when the IGA score of subjects with M1095

treatment held at Week 24 subsequently increases to 1 or more* at which time these subjects will be re-administered the study treatment M1095 at the dose they received prior to Week 24):

- | | | |
|--|---|------------------------------|
| 
 • Placebo at weeks 0, 1, 2, 3, 4, 6, 8, 10 and M1095 120 mg at weeks 12, 14, 16 and Q4W | } | if IGA _{Week24} > 0 |
|--|---|------------------------------|
- | | | |
|---|---|------------------------------|
| 
 • Placebo at weeks 0, 1, 2, 3, 4, 6, 8, 10 and M1095 120 mg at weeks 12, 14, 16 and Q4W until Week 20 and Placebo Q4W* | } | if IGA _{Week24} = 0 |
|---|---|------------------------------|
- | | | |
|--|---|--|
| 
 • M1095 30 mg at weeks 0, 2, 4, 8, 12, and Q4W until Week 20 and Placebo Q4W* | } | if IGA _{Week12} ≤ 1 and IGA _{Week24} = 0 |
|--|---|--|
- | | | |
|--|---|--|

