*** Prior to Week 24**

M1095 subjects in Arms 2 and 3 will receive placebo at Week 1, 3, 6, 10 and 14.
 M1095 subjects in Arm 4 will receive placebo at Week 1, 3, 6, 10, 14 and 16.
 M1095 subjects in Arm 5 will receive placebo at Week 1, 3 and 14.
 Secukinumab subjects in Arm 6 will receive placebo at Week 6, 10 and 14.

Exposure to Placebo will be limited to a maximum of 12 weeks during the induction period and a maximum of 20 weeks after Week 24 (i.e. during the response assessment/dose hold period) provided that the subjects maintain a complete remission (i.e. achieving an IGA = 0).

All subjects, irrespective of whether they completed or discontinued the study, will be followed up for safety and potential sustainability of efficacy, for an additional 8 weeks (56 days) after receiving the last dose of study treatment. In addition, subjects who discontinued prior to Week 52 will be contacted monthly as per the study schedule (up to Week 52) to report any AEs, concomitant medications and any new psoriasis treatments.

2 Interim Analyses

Two Interim Analyses (IAs) are planned during this trial:

1. IA1: the first unblinded IA of complete 12-week data for all randomized subjects will occur at the end of the induction period, while the study is still ongoing,
2. IA2: the second IA will occur at the completion of the maintenance/escalation period at Week 24, while the study is still ongoing.

The purpose of both interim analyses is to closely monitor the safety and tolerability data throughout the study. The study will not be terminated early on the basis of either positive efficacy or futility after the review of the first or the second interim analyses. The two interim analyses are also conducted to gather preliminary efficacy information to make possible executive decisions concerning the clinical project.

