Per-Protocol (PP) including PP12, PP24 and PP48	
The PP populations up to Week 12 and Week 24 will be defined during the blinded data review meeting prior to unblinding at Weeks 12 and 24 respectively. Membership of the PP population after Week 24 will be determined based on new protocol deviations occurring after Week 24.
 
Subjects will be analyzed according to planned treatment:
 
 • in the induction period (up to Week 12) for PP12, • in the maintenance/escalation period (from Week 12 to Week 24) for PP24, • in the response assessment/response hold period (from Week 24 to Week 48) for PP48.
Safety	
The Safety population includes all subjects who receive at least one dose of study treatment.
 
The Safety population will be analyzed per the actual treatment received using a conservative approach that will be described further in Section 4.1.

Pharmacokinetic (PK)	
The Pharmacokinetic (PK) population includes all subjects who receive at least one dose of M1095 with valid (i.e. not flagged for exclusion) PK data and with no occurrence of important protocol deviation impacting the PK results during the study.
 
The PK population will be analyzed per the actual treatment received.

Table 3.1: Definition of Analysis Populations

The primary population for efficacy data will be the ITT population. The primary analysis will be repeated on the M12 and PP12 analysis populations.

Safety data will be analyzed using the Safety population and PK data using the PK population.

All protocol deviations (PDs) will be tracked and their categorization will be reviewed and evaluated during the blinded data review meetings. Important PDs are defined as deviations from the protocol that are likely to have an impact on the subject's rights, safety, well-being, and/or on the validity of the data for analysis. However, only selected clinically important PDs affecting the assessment of efficacy will be excluded from statistical analyses in the PP populations (refer to the supplement to the SAP: Protocol Deviations Exclusion List).

The PP12 and PP24 populations and the PK population will be finalized during the blinded data review meetings.

The precise list of important PDs will be documented and approved at Weeks 12 and 24 before unblinding and at Week 48.

4 Statistical Methods

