4.1 General Considerations

Treatment groups (and their labels to be displayed in Tables, Figures, Listings) are defined as follows:

- for all primary and secondary efficacy analyses and analyses of QoL variables unless otherwise indicated:

Randomized Planned Treatment Group	Treatment Label					
	Induction Period	Maintenance /Escalation Period	Response Assessment/ Dose Hold Period		Final Assessment Period	
			0	12		24
	(in weeks)					
(1) - Placebo at Week 0, 1, 2, 3, 4, 6, 8 (and / M1095 120 mg at Week 12, 14, 16 and Q4W)	Plac/120mg (x4), Q4					
(6) - Secukinumab 300 mg at Week 0, 1, 2, 3, 4, 8 (and 12 and Q4W)	Secukinumab					
(2) - M1095 30 mg at Week 0, 2, 4, 8 (and (2a) Q4W if no escalation at Week 12) (2b) M1095 120 mg Q4W if escalation at Week 12)	30mg (x4), Q4					
(3) - M1095 60 mg at Week 0, 2, 4, 8 (and (3a) Q4W if no escalation at Week 12) (3b) M1095 120 mg Q4W if escalation at Week 12)	60mg (x4), Q4					
(4) - M1095 120 mg at Week 0, 2, 4, 8 (and 12 and Q8W)	120mg (x4), Q8					
(5) - M1095 120 mg Q2W at Week 0, 2, 4, 6, 8, 10 (and 12 and Q4W)	120mg (x6), Q4					

Table 4.1: Randomized Planned Treatment Groups and their Labels for each Treatment Period for Primary, Secondary Efficacy Analyses and Exploratory Analyses of QoL Variables.

- for all safety analyses unless otherwise indicated:

Table 4.2: Actual Treatment Groups for the Induction Period and their Labels for Safety Analyses of the Induction Period

Actual Treatment Group ^a	Treatment Label
	Induction Period (Week 0-12)
(1) - Placebo at Week 0, 1, 2, 3, 4, 6, 8	Placebo
(6) - Secukinumab 300 mg at Week 0, 1, 2, 3, 4, 8	Secukinumab
(2) - M1095 30 mg at Week 0, 2, 4, 8	30mg (x4), Q4
(3) - M1095 60 mg at Week 0, 2, 4, 8	60mg (x4), Q4
(4) - M1095 120 mg at Week 0, 2, 4, 8	120mg (x4), Q8
(5) - M1095 120 mg Q2W at Week 0, 2, 4, 6, 8, 10	120mg (x6), Q4
	Total M1095 ^b

a: Subjects will be assigned to a treatment group based on the actual treatment they received most during the induction period.

b: Total M1095 will include the subjects who receive M1095 treatment during the induction period i.e. (2), (3), (4) and (5).

Table 4.3: Actual Treatment Groups for the Overall Period and their Labels for Safety Analyses of the Overall Period

Actual Treatment Group ^a	Treatment Label
	Overall Period (Week 0-52)
(1) - Placebo at Week 0, 1, 2, 3, 4, 6, 8 (and M1095 120 mg at Week 12, 14, 16 and Q4W)	Plac/120mg (x4), Q4 ^b

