For subjects who have discontinued from M1095/Secukinumab treatment at or prior to the last visit of the induction or maintenance/escalation periods, the duration of exposure will be the sum of the number of days between the date/time of the first dose in the considered period and the date of the last dose before discontinuation and 56 days that correspond to the longest period of washout for M1095/Secukinumab. If the study discontinuation occurred within the 56 days after the last dose received, the duration of exposure will be defined as the difference in days between the date of study discontinuation and the date of first dose of study drug.

Exposure $_{[\text{period } x]} = \text{last dose date/time }_{[\text{period } x]} - 1^{\text{st}} \text{ study drug dose date/time }_{[\text{period } x]} + 56 \text{ days}$.

The treatment exposure of response assessment/dose hold period will be described by several variables:

- the number of subjects who have dose of study drug being withheld at Week 24,
- the duration in days of the dose being withheld during the period i.e. the difference in days between the date of the visit at Week 24 and the date/time of M1095 re-commencement,
- the total duration in days of the dose being withheld since the last dose of M1095 i.e. the difference in days between the date of the last dose of study drug before dose of Week 24 being withheld i.e. at Week 20 and the date/time of M1095 re-commencement (see Table 4.12).

The duration of exposure to M1095/secukinumab treatment overall during the combined induction, maintenance/escalation and response assessment/dose hold periods be calculated as follows:

Secukinumab: Exposure $_{[\text{overall}]} = \text{date/time of last dose} - \text{date/time of } 1^{\text{st}} \text{ dose} + 56 \text{ days}$.

M1095: Exposure $_{[\text{overall}]} = \text{date/time of last dose} - \text{date/time of } 1^{\text{st}} \text{ dose} - d_1 + 56 \text{ days}$.

with the date/time of the first dose as described in Table 4.12 for the different treatment groups and subtracting the dose hold duration for the overall period while considering the 5 half lives of the M1095 treatment (d_1) as explained in Table 4.12. This duration will also be expressed in subject-years by adding the amount of times in days that subjects spent on treatment for all subjects divided by the total number of days in a year i.e. 365.25.

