A subject being administered the complete dose at a given visit is a subject who received the planned number of injections and the planned dosage in mg per injection. A subject being administered the complete dose overall is a subject who received the cumulative number of injections and the cumulative dosage in mg as planned.

A subject will be considered overall compliant for each study period or overall if this subject is missing no more than 20% of the planned treatment and not missing two or more consecutive planned dosing occasions of the considered period or overall. Although subjects will receive two injections at each visit, the two injections at the same visit will be regarded

as a single dosing occasion. If a subject misses two injections at a visit, this subject will be reported as missing the dosing occasion at this visit.

Table 4.12: First M1095 Dose and Calculation of Dose Hold Duration Depending on Treatment Group

Actual Treatment Group	First Dose	Total Dose Hold Duration (d) since last dose of study drug (in days)	Dose Hold Duration for Overall Period (d ₁) (in days) If d-56 < 0, d ₁ = 0
(1) – Placebo at Week 0, 1, 2, 3, 4, 6, 8 (and (1.i) M1095 120 mg at Week 12, 14, 16, 20 and dose hold from Week 24)	Week 12	d = M1095 Restart – Week 20*	d ₁ = d – 56
(1.j) M1095 120 mg at Week 12, 14, 16 and Q4W	Week 12	N/A	d ₁ = 0
(2) - M1095 30 mg at Week 0, 2, 4, 8 (and (2b) M1095 120 mg Q4W if escalation at Week 12)	Week 0	N/A	d ₁ = 0
(2a.i) Q4W and dose hold from Week 24)	Week 0	d = M1095 Restart – Week 20*	d ₁ = d – 56
(2a.j) Q4W)	Week 0	N/A	d ₁ = 0
(3) - M1095 60 mg at Week 0, 2, 4, 8 (and (3b) M1095 120 mg Q4W if escalation at Week 12)	Week 0	N/A	d ₁ = 0
(3a.i) Q4W and dose hold from Week 24)	Week 0	d = M1095 Restart – Week 20*	d ₁ = d – 56
(3a.j) Q4W)	Week 0	N/A	d ₁ = 0
(4) - M1095 120 mg at Week 0, 2, 4, 8 (and (4.i) 12 and Q8W and dose hold from Week 24)	Week 0	d = M1095 Restart – Week 20*	d ₁ = d – 56
(4.j) 12 and Q8W	Week 0	N/A	d ₁ = 0
(5) - M1095 120 mg Q2W at Week 0, 2, 4, 6, 8, 10 (5.i) 12 and Q4W and dose hold from Week 24)	Week 0	d = M1095 Restart – Week 20*	d ₁ = d – 56
(5.j) 12 and Q4W	Week 0	N/A	d ₁ = 0
(6) - Secukinumab 300 mg at Week 0, 1, 2, 3, 4, 8 (and 12 and Q4W)	Week 0	N/A	N/A

*If a subject missed the dose of Week 20, the last visit of the maintenance/escalation period when the subjects were injected the study drug will be considered instead of Week 20.

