4.9.2.5 Adverse Events

Treatment-Emergent AEs (TEAEs) per treatment period are AEs that emerge while on study treatment during a given treatment period (e.g. induction period), having been absent pre-treatment, or that worsen during the considered period (e.g. induction period) relative to the pre-treatment state i.e. after baseline and on or prior to the date of the last visit of the considered period (e.g. Week 12 for the induction period). On study treatment during a treatment period is defined as the period from the first study treatment administration at the start of period (e.g. Week 0 for the induction period) up to the last visit of the treatment period for subjects who did not discontinue treatment during the considered period (e.g. Week 12 for the induction period) or for subjects who discontinued during the considered period, up to the end of the considered period or up to 8 weeks after the last dose of study treatment, whichever occurs first. TEAEs will be assigned to the actual treatment period to which they are considered treatment-emergent.

When considering the study overall, treatment-Emergent AEs (TEAEs) are AEs that emerge while on study treatment i.e. from the first study treatment administration up to 8 weeks after the last dose of study treatment, having been absent pre-treatment, or that worsen during study treatment relative to the pre-treatment state i.e. after baseline.

If the classification of an AE cannot be clearly established because of missing or incomplete date/time of AE, the AE will be classified as treatment-emergent. No imputation of missing or partial AE start and end dates will be performed.

To determine whether an AE is pre-treatment, on-treatment or post-treatment in case of partial or missing AE dates, the rules below will be followed:

- If the start date is incomplete and either the end date is incomplete or available:
 - if the non-missing part of the start date infers that the AE occurred post-treatment, the AE will be considered as post-treatment.
 - If the partial or complete end date indicates that the AE occurred prior to the first dose of study drug, the AE will be considered as pre-treatment.
 - If the partial start date does not give any evidence as to when the AE occurred during the study, and the end date infers that the AE stopped after the first dose of study drug, the AE will be flagged as on-treatment for all periods for which the first dose of study drug was started before the end of the AE.

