 - If the partial or complete start and end dates do not indicate as to when the AE started and ended compared to the first dose of study drug of any period, the AE will be flagged on-treatment for all periods.
- If both start and end dates are both missing: the AE will be considered on-treatment and therefore a TEAE for all periods.

To determine the worsening of an AE during study treatment, the maximum severity for each AE during the baseline period will be considered. In case of missing severity, the conservative approach below will be followed:

- If an AE has a missing severity during the study treatment, it will be defined as treatment-emergent.

- If the severity of an AE is missing at baseline and this event continues during the study treatment, this AE will be considered as treatment-emergent.

Adverse events of Special Interest (AESI) include cytopenias, liver function test changes/enzyme elevations, infections, injection-site reactions, allergic/hypersensitivity reactions, cerebrocardiovascular events, malignancies, depression, Crohn's disease and ulcerative colitis. Additional adverse events may be identified as being of special interest during the study and prior to first unblinding.

An overview table will present the number and percentage of subjects experiencing these types of AEs below by treatment:

- TEAEs,
- TEAEs by relationship to investigational product,
- serious TEAEs including deaths,
- TEAEs by maximum severity,
- deaths,
- and TEAEs leading to study treatment discontinuation.

This table will be produced for all separate treatment periods and the overall periods (refer to Table 4.3, Table 4.13, Table 4.14 and Table 4.15).

For the overall period, the exposure-adjusted incidence per 100 subject-years will also be presented. The exposure-adjusted incidence will be calculated by dividing the number of subjects with AEs by the total person years of exposure during the treatment period (refer to Section 4.7). This result will be multiplied by 100 to obtain the exposure-adjusted incidence per 100 subject-years.

The AESI will also be displayed with an overview table by treatment for each treatment period and the overall periods.

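### The overall exposure-adjusted AE rate drops long dose-hold days from M1095 person-time but still counts AEs that start in them, and no rule covers held subjects who never restart (minor)

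*SAP*

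**What the plan says.** **Denominator.** For M1095, SAP 4.7.1 defines overall exposure as last dose minus first dose minus d1 plus 56 days, "subtracting the dose hold duration for the overall period while considering the 5 half lives of the M1095 treatment". Table 4.12 sets d, the total hold since the last dose, to "M1095 Restart – Week 20" for every held group. It then sets d1 = d − 56, with d1 = 0 when that is negative. Its only footnote covers a missed Week 20 dose. The secukinumab formula has no subtraction.

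**Numerator.** In SAP 4.9.2.5, overall treatment-emergent AEs are those that emerge or worsen "from the first study treatment administration up to 8 weeks after the last dose of study treatment". Nothing in that section takes out the hold.

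**Rate.** The same section obtains the overall-period incidence by "dividing the number of subjects with AEs by the total person years of exposure during the treatment period", points to Section 4.7 for the exposure, and scales to 100 subject-years.

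**Other wording that bears on the point.**
- The exposure list that opens SAP 4.7.1 describes treatment exposure, in days and in subject-years, as including dose-hold time. It explains subject-years as the number of subjects multiplied by years on treatment. Later in the section, subject-years are summed days divided by 365.25.
- SAP 1.4 says that non-escalated M1095 subjects who "achieve an IGA score of 0 at Week 24 will have the study treatment withheld" and then receive placebo. Below Figure 1.1 it limits later placebo exposure to "a maximum of 20 weeks after Week 24 (i.e. during the response assessment/dose hold period", provided that IGA stays at 0. Subjects who never restart are therefore foreseen.

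**The concern.** The numerator and denominator of a rate should cover the same time at risk. Here a held subject who restarts late can contribute an AE from days that contribute no person-time. The 56-day washout does not explain the gap, because it is credited before d1 starts to accrue.

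The error has one direction. Take the AEs as counted: putting the hold days back enlarges the denominator. Take the denominator as defined: restricting AEs to it can only reduce the numerator. On either matched basis the M1095 rate falls or stays the same. Secukinumab is unaffected, so a side-by-side reading is tilted against M1095. Held shares and restart times may also differ by regimen, so the M1095 arms need not be affected equally.

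A second gap concerns subjects who never restart. With no restart date, d has no value. The two hold durations that 4.7.1 asks for also end at re-commencement, so they have none either.

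**Working it through.** **Check of the plan's own figure.** The 56 days stand for five half-lives. Protocol 2.3 gives a terminal half-life of 11 to 12 days: 5 × 11 = 55 and 5 × 12 = 60 days. The 56 days (8 weeks) are consistent with that.

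**Inputs.** Last scheduled dose at Week 44 (Protocol 6.7). Last pre-hold M1095 dose at Week 20 (SAP Table 4.12). First dose counted at Week 0 for Arms 2 to 5 and Week 12 for Arm 1 (Table 4.12; Table 4.3, footnote b). Visits are taken on schedule.

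**Formulas.**
- AE window W = (44 − first week) × 7 + 56. Arms 2 to 5: 308 + 56 = 364 days. Arm 1: 224 + 56 = 280 days.
- d = (restart week − 20) × 7; d1 = max(0, d − 56); exposure E = W − d1.

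| Restart week | d | d1 | E, Arms 2–5 | W/E | E, Arm 1 | W/E |
|---|---|---|---|---|---|---|
| 28 | 56 | 0 | 364 | 1.00 | 280 | 1.00 |
| 32 | 84 | 28 | 336 | 1.08 | 252 | 1.11 |
| 36 | 112 | 56 | 308 | 1.18 | 224 | 1.25 |
| 40 | 140 | 84 | 280 | 1.30 | 196 | 1.43 |
| 44 | 168 | 112 | 252 | 1.44 | 168 | 1.67 |

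W/E is the inflation against a rate that keeps hold days in both parts.

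**Against a rate that excludes hold days from both parts**, the inflation is smaller. Let f(T) = 1 − exp(−hT/365.25) be the chance of at least one AE in T days at an assumed constant hazard h. For a Week 36 restart in Arms 2 to 5, f(364)/f(308) = 1.14 at h = 0.5 per year and 1.06 at h = 2.

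**Arm level.** Let q be the share of the arm restarting at Week 32 or later and d1 their mean removed time. The documents give neither. With full follow-up and the Table 4.3 grouping, inflation = W / (W − q × d1).
- Arms 2 to 5: q = 0.1, d1 = 28 gives 364/361.2 = 1.01; q = 0.4, d1 = 84 gives 364/330.4 = 1.10.
- Arm 1: the same inputs give 280/277.2 = 1.01 and 280/246.4 = 1.14.

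**Never-restarters.** The result depends on which dose counts as last and how far d runs.

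| Reading of exposure | E, Arms 2–5 | 364/E | E, Arm 1 | 280/E |
|---|---|---|---|---|
| Last M1095 dose (Week 20), d1 = 0 | 196 | 1.86 | 112 | 2.50 |
| Last placebo dose (Week 44), d to Week 44 | 252 | 1.44 | 168 | 1.67 |
| Last placebo dose, d to Week 48 | 224 | 1.63 | 140 | 2.00 |
| Last placebo dose, d to Week 52 | 196 | 1.86 | 112 | 2.50 |
| Last placebo dose, d1 = 0 | 364 | 1.00 | 280 | 1.00 |

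The ratios assume that the AE window runs to the last placebo dose plus 56 days. If it ends at the last M1095 dose plus 56 days, the first row becomes 196/196 and 112/112, both 1.00.

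**The case against.** **Exposure may be meant to include the hold.** SAP 4.9.2.5 refers to Section 4.7 as a whole, and 4.7.1 opens by describing exposure as including dose-hold time. On that reading the mismatch disappears. But the only explicit formula for overall M1095 exposure subtracts d1, and Table 4.12 exists to compute it. What stands is a conflict within 4.7.1 that also needs resolving.

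**Removing off-drug time is defensible.** A rate per time under drug is a sensible target, and this stands as a reason for the denominator. It does not justify a numerator that covers more time.

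**The never-restarter gap is largely answered elsewhere.** Protocol 6.0 defines study drug to include placebo. SAP Section 3 states that "The Safety population includes all subjects who receive at least one dose of study treatment" and Table 4.2 reports a placebo group, so placebo counts as study treatment during induction. This favours an AE window that runs to the last hold placebo. Against it, SAP 1.4 calls treatment withheld while placebo is given, and Table 4.12 uses last dose of study drug for the last M1095 dose. Using either dose consistently with d1 = 0 gives a ratio of 1.00. What stands is a missing rule, not a demonstrated bias. A reader might infer that 1.86 or 2.50 is the effect of the plan, but these are only the top of a range that starts at 1.00.

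**The consequence is small.** The rate is descriptive, SAP 4.9 plans no formal safety comparison, and the bias runs against the sponsor's own product. This stands and limits the severity.

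**Conclusion.** The late-restarter mismatch follows from explicit SAP text. It is wrong as written and minor. Per subject it is 1.00 for a Week 28 restart, rising to 1.44 for a Week 44 restart (Arm 1: 1.67). The arm-level figures of 1.01 to 1.10 and 1.01 to 1.14 rest on assumed shares and durations, no early discontinuation, and the Table 4.3 grouping. They do not carry over to Table 4.13, where escalated subjects contribute only Weeks 0 to 12 to the 30 mg and 60 mg groups.

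The two parts differ in reach. The late-restarter mismatch affects only the exposure-adjusted rate. The meaning of last dose of study treatment for never-restarters goes further. If their window closed at Week 28 (Week 20 plus 8 weeks), later AEs would also leave the overall treatment-emergent counts and percentages. By-period AE tables are unaffected, because their windows run to the last visit of the period for subjects who did not discontinue. Efficacy is unaffected.

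A reader might infer that all held subjects inflate the rate, or that the safety comparison with secukinumab is invalid. The documents support neither: a Week 28 restart loses no days, and no formal comparison is planned.

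**What to change.** 1. Use the same at-risk time in the numerator and denominator of this rate, by one of two routes:
   - Count only AEs with onset inside the person-time of 4.7.1, and list AEs from the d1 days separately. The drawback is that a subject-count rate over a shorter window is still not fully comparable with unheld arms. For a Week 36 restart in Arms 2 to 5, [f(308)/308] / [f(364)/364] = 1.04 at an assumed 0.5 AEs per year and 1.12 at 2 per year.
   - Keep hold days in both parts. The drawback is that off-drug time can dilute the M1095 rate against continuously dosed secukinumab.

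   The choice depends on what the rate is meant to describe, and the SAP should say so.
2. Reconcile the opening list of 4.7.1 with the overall formula, and keep one definition of subject-years (summed days divided by 365.25).
3. For held subjects who never restart, state one end date and use it for both exposure and the overall treatment-emergent window.
4. Say in 4.9.2.5 whether hold-period placebo counts as study treatment.

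The cost is SAP wording and a small programming change on dates already collected. Under the first route, AEs from the excluded days move to a separate line.
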